3. EXPECTED RISKS AND BENEFITS

Expected risks:

Anticipated risks of this study are estimated to not more than that in standard clinical care as no interventions are done to the subject's treatment.

There may be minimal risk associated with blood sampling. Blood samples will be taken from established blood vessel access in order to minimise discomfort from the patients. In the event where blood-sampling is done directly from a vein, it is possible that some bruising or bleeding may occur at the site where the blood is drawn. There is also a rare chance that inflammation or infection may occur at the sites of blood withdrawal.

There may be a risk of breach of confidentiality but the risk is low. Only members of the study team will be involved in the extraction of the clinical information and laboratory results. Identifying data, e.g., name and NRIC number will be kept separately from other clinical information in the database. The database will be password-protected and can only be accessed by members of the study team.

Expected Benefits:

Clinical outcomes in this study will be similar to that of standard clinical care as no interventions are done to the subject's treatment. Attending physicians will have the option of knowing the results and decide on their own discretion whether to make any dose adjustments to optimise beta-lactam therapy, based on the suggestion of an infectious disease trained pharmacist.

Data derived can be used to build pharmacokinetic models and derive subsequent individualised optimal dosing regimen to improve clinical outcomes.

4. STUDY POPULATION

4.1. List the number and nature of subjects to be enrolled.

Patients will be recruited until 320 assays are performed (based on budget of \$40,000, estimated cost of each assay is \$125, number of assays = 40,000/125 = 320 assays). This will be roughly equivalent to 80 patients, assuming patients will have 4 assays each. There will be no restriction on race or gender.

4.2. Criteria for Recruitment and Recruitment Process

Patients, admitted to intensive care units/intensive care areas/high dependency wards/burs department/haematology department/oncology department/renal department/infectious disease department, and are initiated on beta-lactam therapy will be identified from pharmacy dispensing records and screened for eligibility. Physicians may also refer patients to the study team.

4.3. Inclusion Criteria

- a) Age ≥ 21 years old
- b) Admitted to Singapore General Hospital
- c) Receiving beta-lactams for documented or suspected infection
- d) With indication for beta-lactam TDM: critically ill, altered pharmacokinetics (burns, obese, on extracorporeal therapy e.g. dialysis), immunocompromised (haematology/oncology patients), resistant pathogens, deep-seated infections, suspected

or at risk for adverse effects

4.4. Exclusion Criteria

- a) Pregnancy
- b) Expected mortality within 24 hours

5. STUDY DESIGN AND PROCEDURES/METHODOLOGY

This is a prospective observational study conducted in Singapore General Hospital from October 2019 to September 2020. Patients will be screened for eligibility using criteria 4.3 and 4.4. If women of childbearing age are eligible, the beta HCG result taken during the potential subject's course of hospitalisation will be used to exclude pregnant women. If no beta HCG result is available, clinical case notes will be referred to confirm non-pregnancy status.

Eligible patients will be approached by their treating physicians to seek their consent to be referred to the study team. Informed consent will be taken directly from the patient by the study team once patient is agreeable to be referred to the study team. For subjects who do not have the mental capacity to exercise rational judgement, primary physician will assess and document their mental capacity using the Documentation of Capacity form and substituted consent will be obtained by the study team from the spouse, parent, guardian, or legally acceptable representative of the subject. Consent for continued participation will be obtained from patient directly when he regains mental capacity to give informed consent.

Blood sampling and data collection will only commence once informed consent has been taken. Subjects may withdraw voluntarily from participation in the study at any time. Once they have withdrawn from the study, all subsequent blood sampling and data collection will be discontinued.

All patients will be followed up until end of beta-lactam therapy, 30 days from commencement of beta-lactam therapy, hospital discharge or mortality, whichever occurs later.

Blood sampling:

For all patients, 4 sets of blood samples (5 mL each) will be obtained via venipuncture or existing cannula access within a dosing interval. We propose to obtain 4 samples for each TDM in this study to generate more robust and accurate drug concentration-time curves for calculation of target attainment and to better characterise patients' pharmacokinetic profiles. For most patients (except those on intermittent extracorporeal therapies), blood samples will be obtained during end of infusion, 1 hour after infusion, 2 hours after infusion and within 30 minutes of the next scheduled dose (i.e. trough level) if beta-lactam is given as short infusion over \leq 30 minutes. If beta-lactam is given as extended infusion (e.g. 3-4 hours), blood samples will be obtained at mid-infusion, end of infusion, 1 hour after infusion and within 30 minutes of the next scheduled dose (i.e. trough level). For patients on intermittent extracorporeal therapies (e.g. intermittent dialysis), blood samples will be obtained at end of beta-lactam infusion, at the beginning of dialysis, end of dialysis and within 30 minutes of the next scheduled dose (i.e. trough level).

To ensure therapeutic targets are reached, further blood sampling, according to the schedule above, may be performed after dose adjustments or when there is a change in patient's clinical status (e.g. change in dialysis settings, change in renal function), which may warrant change in beta-lactam dosing regimen. Blood sampling for TDM will be stopped when beta-lactam has been discontinued, when therapeutic targets are achieved or when patient has been discharged from the hospital.

Assay of beta-lactam levels

All blood samples will be sent to our research laboratory for assay via liquid chromatographytandem mass spectrometry. All blood samples will be labelled by our study team using subject codes (no patient identifiers will be used).

Beta-lactam TDM and Dose Individualisation

The treating physicians will have the option to know the results of the TDM, once available. An infectious disease-trained pharmacist may make recommendations on dose adjustments based on the TDM results. However, accepting these recommendations will be at the discretion of the treating physicians.

The infectious disease trained pharmacist may use pharmacokinetic software to analyse drug concentration-time profile to guide dose adjustments. If available, dose recommendations will be based on the MIC of the known pathogen, which will be provided by the local microbiology laboratory. Where no pathogen was formally identified, MICs are not available or cultures are pending, the highest MIC (according to the Clinical and Laboratory Standards Institute (CLSI criteria) for susceptible bacteria to the antibiotic will be assumed.

Data Collection

All patients will be followed up from study entry to 30 days from study entry, hospital discharge or mortality, whichever occurs earlier.

Data will be collected from electronic medical records, using a standardised data collection form. These will include:

•patient demographics (unique identifier, age, gender, race, body weight, height, comorbidities including Charlson Comorbidity Index)

•pharmacokinetic-specific data (use of extracorporeal therapy/dialysis and settings, urine output, serum creatinine, albumin)

•clinical data (temperature, blood pressure, heart rate, respiratory rate, mortality, cause of mortality, severity of illness indicators such as APACHE II score and SOFA score, incidence of beta-lactam-related adverse events/side effects as reported by primary physicians, admission and discharge date from hospital and from intensive care unit if applicable)

•laboratory data (albumin, serum creatinine, procalcitonin, CRP, total white count)

•infection-related data (site and type of infection, pathogens isolated and their susceptibility results and reported minimum inhibitory concentrations)

•drug-related data (beta-lactam dosing regimens including any change to dosing regimens, concurrent antibiotic use history and their dosing regimens, presence of any drug which may interact with beta-lactams or interfere with beta-lactam assay results)

•beta-lactam assays levels, attainment of therapeutic targets and whether dose adjustments were made

Data will be stored in a password-protected database and only study team members will have access to data. Identifiers will be stored separately from collected data. Data collection forms will not contain identifiers (e.g. NRIC, name, date of birth). All hardcopy data collection forms and consent forms will be stored under lock and key in the cupboard at [name] of

Pharmacy department in Singapore General Hospital.

Based on SingHealth Cluster Research Data Management Policy – Clinical Trial and Clinical Research, research data will be retained in a secured storage facility (mentioned in section R1(i) for a minimum of 7 years after completion of research study or date of publication of the research using the research data, whichever is later. The data collected will be also stored and used for future research.

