8.2. Statistical and Analytical Plans

Our primary outcome will be attainment of beta-lactam therapeutic targets: 100%fT>MIC, 40-70%fT>5xMIC, 100%fT>5xMIC. Proportion of patients, who achieve beta-lactam therapeutic targets, during the first and subsequent TDM will be determined. For the group of patients, who require dose adjustments, after the 1st TDM and need further TDM, the proportion of patients who require dose increment and dose reduction, the number of TDM performed to achieve therapeutic target and the mean/median time required to achieve therapeutic target will also be evaluated.

Correlation of primary outcomes will be made to the following secondary outcomes.

- a. Mortality at the end of therapy and within 30-day mortality.
- b. Days to defervescence
- c. Days to resolution of white blood cell count, pro-calcitonin and C-reactive protein.

Any incidence of adverse effects related to beta-lactam therapy will also be reported and evaluated in correlation to beta-lactam levels.

For univariate analyses with binomial outcomes (e.g. mortality), Chi-square test or Fisher's exact test will be performed where appropriate. For univariate analyses with time-dependent outcomes (e.g. days to defervescence, days to resolution of inflammatory markers), Kaplan-Meier analysis will be performed. For univariate analyses with continuous outcome variables (e.g. APACHE II score, SOFA score), Student's t-test and Mann-Whitney-U test will be performed for parametric and non-parametric data respectively. Multivariate analyses will then be performed to include potential confounders such as APACHE II score, SOFA score, Charlson comorbidity index, use of beta-lactam as culture-directed therapy, presence of multi-drug resistant infection, and presence of concurrent infections requiring additional antibiotics. Logistic regression will be used for binomial outcomes (mortality) while Cox regression will be used for time-dependent outcomes (days to defervescence, days to resolution of inflammatory markers).

To evaluate population pharmacokinetics in various patient groups, a specialised pharmacokinetic software will be used to develop population pharmacokinetic models. Model simulation will then be performed to design empiric dosing recommendations to guide local practice.

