11.1. Informed Consent

Patients eligible for the study will be first approached by their treating physicians for consent to be referred to the study team.

For critically ill patients who are unable to give consent, documentation of mental capacity will be made by primary physician and consent from patients' spouse, parent, guardian or LAR will sought before study team approach them. Informed consent will be obtained from the spouse, parent, guardian or LAR using the substituted consent form. Once patient has regained capacity to give informed consent, their consent for continued participation will be obtained using the continued participation consent form.

Informed consent will then be taken by a designated member of the study team in a quiet area at an appropriate time when the patient or his / her spouse, parent, guardian or LAR will not be interrupted by other healthcare workers, patients or visitors. The objectives, study procedures, risk and benefits will be explained and any questions will be answered.

Informed consent will be obtained from English-speaking patients and/or his/her representatives only.

All informed consents will be held in the presence of a witness. All patients will be given sufficient time to make a decision.

While obtaining and documenting informed consent, the study team members will comply with the SGGCP guidelines and to the ethical principles that have their origin in the Declaration of Helsinki.

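### Withdrawal stops record-based follow-up as well as blood sampling, and the plan does not say what follows if a patient who regains capacity declines to continue

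*Combined protocol and SAP*

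**What the plan says.** Section 5 lets any subject leave: "Subjects may withdraw voluntarily from participation in the study at any time". The consequence follows directly: "Once they have withdrawn from the study, all subsequent blood sampling and data collection will be discontinued". The visible text offers no level at which sampling stops and follow-up through the record goes on.

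Under Data Collection, the same section gives the source of the data: "Data will be collected from electronic medical records, using a standardised data collection form". The items listed include mortality, temperature, white cell count, procalcitonin and CRP, which are the raw material for the secondary outcomes.

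Patients without capacity enter by substituted consent. Section 5 then requires a second step: "Consent for continued participation will be obtained from patient directly when he regains mental capacity to give informed consent". Section 11.1 repeats it: "Once patient has regained capacity to give informed consent, their consent for continued participation will be obtained using the continued participation consent form". Neither section says what happens to sampling or data if the patient declines.

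Section 8.2 lists "Mortality at the end of therapy and within 30-day mortality" among the secondary outcomes, together with time to defervescence and time to resolution of the markers. Mortality goes into logistic regression, and the time outcomes into Kaplan-Meier and Cox analyses. The section has no rule for missing or withdrawn outcomes.

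**The concern.** The burden that participation adds is blood: four 5 mL samples per TDM, with further sets possible. The outcome data cost the patient nothing extra. A rule that ends both together discards information that could be kept with the patient's agreement.

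The re-consent step adds a possible selection. A patient who dies without regaining capacity never reaches it and keeps a complete record. Only patients alive and well enough to decide can decline there. If declining ends data collection, missing outcomes at this step would be concentrated among patients doing better.

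Three results are exposed:
- **Mortality.** A complete-case proportion could be too high.
- **Time outcomes.** Kaplan-Meier and Cox assume that a censored patient has the same prospects as those still followed. Return of capacity plausibly accompanies clinical recovery, so censoring at that moment may be informative and could make recovery look slower.
- **Association with attainment.** This is the first secondary objective. Section 5 stops TDM sampling once targets are reached and allows repeats after dose adjustment, so non-attainers may face more draws. Refusal could therefore differ by attainment.

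**Working it through.** **The plan's own figure.** Section 8.1: 40,000/125 = 320 assays, and 320/4 = 80 patients. Both reproduce. No allowance for withdrawal is given.

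**Inputs.** N = 80 is from Section 8.1. The documents give none of the following, so all are assumptions:
- s, share entered by substituted consent: 25-50%
- m, mortality, taken as equal in all patients: 20-40%
- g, share of surviving substituted-consent patients who regain capacity: 80%
- r, share of those who decline to continue: 5-30%

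The illustration also assumes that a refusal ends data collection, that everyone who refuses survives, and that mortality is computed on complete cases.

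**Formulas.** Lost = N × s × (1 − m) × g × r. Observed mortality = N × m / (N − lost).

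Example with s = 50%, m = 30%, r = 20%: lost = 80 × 0.5 × 0.7 × 0.8 × 0.2 = 4.48. Observed = 24/75.52 = 31.8%, against a true 30.0%.

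| s | m | r | Lost | Observed mortality | Shift (points) |
|---|---|---|---|---|---|
| 25% | 40% | 5% | 0.5 | 32/79.52 = 40.2% | +0.2 |
| 25% | 20% | 5% | 0.6 | 16/79.36 = 20.2% | +0.2 |
| 50% | 30% | 20% | 4.5 | 24/75.52 = 31.8% | +1.8 |
| 50% | 20% | 30% | 7.7 | 16/72.32 = 22.1% | +2.1 |
| 50% | 40% | 30% | 5.8 | 32/74.24 = 43.1% | +3.1 |

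Over the whole grid, 0.5 to 7.7 survivors are lost and mortality rises by 0.2 to 3.1 points.

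**Within the substituted-consent group alone** the shift is larger. Take 40 such patients with 12 deaths (30%), all 28 survivors regaining capacity, and 10% or 25% of them declining (2.8 or 7 patients). Observed mortality is 12/37.2 = 32.3% or 12/33 = 36.4%. Spread over 80 patients with 24 deaths, the same losses give 24/77.2 = 31.1% or 24/73 = 32.9%.

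**Association with attainment.** Assume 40 attainers with 8 deaths and 40 non-attainers with 16 deaths. The true odds ratio is (8 × 24)/(32 × 16) = 0.375. With s = 50% and g = 80% in both groups, survivors are multiplied by 1 − 0.4r.
- Equal refusal (10% or 20% in both groups): the factor cancels and the odds ratio stays at 0.375.
- 20% in attainers, 5% in non-attainers: survivors are 32 × 0.92 = 29.44 and 24 × 0.98 = 23.52. Odds ratio = (8 × 23.52)/(29.44 × 16) = 0.399.
- 5% and 20% the other way round: survivors are 31.36 and 22.08. Odds ratio = (8 × 22.08)/(31.36 × 16) = 0.352.

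**Time outcomes.** The documents give nothing from which to size the effect of informative censoring, so none is computed.

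**The case against.** Stopping everything at withdrawal is a cautious choice that respects consent, and several limits on the concern stand.

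- **A reader might infer that outcomes are, as a fact, lost selectively from survivors.** The documents do not support that. It needs refusals to occur and to be handled as withdrawal, and Sections 5 and 11.1 state neither. Any subject may withdraw at any time, including patients with capacity who later die. A patient who regains capacity, declines and then dies before day 30 is a lost death.
- **A reader might also infer that turning down one more blood draw costs the patient all follow-up.** Section 5 describes repeat sampling as optional and does not equate a refused draw with withdrawal.
- **The consent forms were not available for review.** They may already offer record-only follow-up.
- **The planned mortality analysis is an association.** Equal refusal leaves the odds ratio unchanged, and a difference by attainment is conjecture.
- **Kaplan-Meier and Cox keep each patient's time up to censoring.** Informative censoring is plausible, but its size and direction are not shown.
- **The follow-up conflict may cost more 30-day data.** One sentence in Section 5 runs follow-up to the end of therapy, "30 days from commencement of beta-lactam therapy, hospital discharge or mortality, whichever occurs later". Another, under Data Collection, takes the earliest of day 30 from study entry, discharge or death. Under the second, a patient discharged alive before day 30 is followed no further, whatever the withdrawal rule.

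These points reduce the size and certainty of the bias. They do not remove the explicit rule that ends record-based collection, or the silence on a declined continued-participation consent.

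**Conclusion.** The point holds as an avoidable loss of secondary-outcome data with a possible, conditional bias. The stop on data collection is stated in the plan. Selective loss at re-consent is a tendency that follows from who is asked, and it depends on refusals occurring and being handled as withdrawal.

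On the assumed rates, the effect on whole-cohort mortality is small to modest, about 0.2 to 3 percentage points upward. The odds ratio moves only under unequal refusal, for example from 0.375 to 0.352 or 0.399. Target attainment at the first TDM, part of the primary outcome, is largely unaffected because only later data stop. The change is still worth making: the sample is about 80 patients, Section 8.2 names six confounders for adjustment, and the data are already in the record.

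**What to change.** Replace the Section 5 sentence with two levels of withdrawal:

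(a) blood sampling stops, but outcomes continue to be collected from the record to the end of follow-up;

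(b) full withdrawal, with data already collected kept where consent and local rules permit.

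Offer the same choice at the continued-participation consent, and state in Sections 5 and 11.1 what a refusal there means. Record the level chosen and its date. In Section 8.2, keep level (a) patients in all outcome analyses and say how missing outcomes from level (b) are handled. Reconcile the two follow-up sentences in Section 5, since level (a) needs one defined end point.

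The cost is an ethics amendment and consent-form wording, if the forms do not already offer this. No extra visits or samples are needed. Patients who choose (b) are still lost.

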To address the gaps in evidence above, we propose a prospective observational study to evaluate the feasibility of beta-lactam TDM in the local setting. Our target population will be adult patients (21 years old and above), admitted to Singapore General Hospital, are receiving beta-lactams for documented or suspected infection and belong to the following group of patients who will most benefit from beta-lactam TDM: i.e. critically ill patients (admitted to intensive care units, intensive care areas, high dependency wards), haematology/oncology patients, burns patients, patients with extracorporeal therapies which will alter beta-lactam pharmacokinetics (e.g. extracorporeal membrane oxygenation, dialysis), patients with resistant infections or deep-seated infections requiring high dose beta-lactam therapy and patients, who are suspected or at risk of developing beta-lactam adverse effects. We will prospectively collect four blood samples over a dosing interval from each patient. The beta-lactam levels will be assayed using liquid chromatography with tandem mass spectrometry. Attending physicians will have the option of knowing the results and whether to accept dose adjustments recommendations by trained infectious disease pharmacist. Proportion of patients attaining therapeutic targets during the first and subsequent TDM will be evaluated. Patients will also be followed up for clinical outcomes such as mortality and clinical response.

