2. HYPOTHESIS AND OBJECTIVES

We hypothesise that current licensed beta-lactam dosing regimens are suboptimal in at least half our patients: patients with severe sepsis in intensive care units/high dependency wards, burns patients, patients requiring dialysis and other forms of extracorporeal therapy, haematology/oncology patients, and patients with resistant pathogens or deep-seated infections requiring high dose beta-lactam therapy. Hence, beta-lactam TDM would be necessary for these patients to optimise their dosing regimens and improve their clinical outcomes.

Our primary objective is to evaluate proportion of sub-optimal beta-lactam levels in correlation to MIC and the need for dose adjustments

Our secondary objectives include:

- 1. Correlating the achieved pharmacokinetic/pharmacodynamic therapeutic targets (100%T>MIC, 40-70%T>5xMIC, 100%T>5xMIC) with clinical outcomes (mortality, clinical response, microbial eradication) in the different sub-groups mentioned above
- 2. Characterising beta-lactam pharmacokinetics (as exploratory analysis) for certain patient populations, with limited beta-lactam pharmacokinetics characterised in primary literature (e.g. those requiring extracorporeal therapy, various types of dialysis), to aid design of empiric dosing regimens suitable for local practice.

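### Section 5 gives two contradictory follow-up rules for all patients; under one of them, patients discharged alive before day 30 have no planned status for 30-day mortality in any location

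*Combined protocol and SAP*

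**What the plan says.** Both rules stand in the current text of Section 5.

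- **Opening design text, just before the blood-sampling schedule:** follow-up runs to the end of beta-lactam therapy, "30 days from commencement of beta-lactam therapy, hospital discharge or mortality, whichever occurs later".
- **Data Collection:** "All patients will be followed up from study entry to 30 days from study entry, hospital discharge or mortality, whichever occurs earlier". The sentence after it names the only data source: "Data will be collected from electronic medical records, using a standardised data collection form".

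The outcomes that depend on follow-up appear elsewhere. Section 1 makes a general promise with no window: "Patients will also be followed up for clinical outcomes such as mortality and clinical response". The first secondary objective in Section 2 relates the pharmacokinetic/pharmacodynamic targets "with clinical outcomes (mortality, clinical response, microbial eradication) in the different sub-groups mentioned above". Section 8.2 lists "Mortality at the end of therapy and within 30-day mortality" among the secondary outcomes and treats mortality as binary: "For univariate analyses with binomial outcomes (e.g. mortality), Chi-square test" or Fisher's exact test, followed by logistic regression with confounders.

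No section says which follow-up rule governs, from which date the 30 days in Section 8.2 are counted, whether a death after discharge counts, or how a patient discharged alive before day 30 is to be classified.

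**The concern.** The two rules cannot both be followed. They differ in direction (last event against first event), in time origin (start of therapy against study entry), and in whether the end of therapy counts at all.

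A binary 30-day mortality outcome needs each patient's status on day 30. Under the Data Collection rule, follow-up of a patient who goes home on day 12 ends on day 12. If the outcome means death in any location, the plan provides no day-30 status for that patient. Status at the end of therapy is lost in the same way when therapy outlasts discharge or day 30 from entry.

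The loss is selective, because the discharge rule removes only patients who left hospital alive. With two rules in force, the reported figure could be 30-day mortality, in-hospital mortality or a mixture. Mortality is one of the outcomes against which the targets are to be compared, so an unclear definition carries through to that comparison.

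**Working it through.** **The plan's own figure.** Sections 4.1 and 8.1: 40,000/125 = 320 assays; 320/4 = 80 patients. This reproduces. It is a budget figure and only approximate: repeat monitoring lowers the number of patients and incomplete sample sets raise it.

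**The two rules applied to example patients.** Day 0 is the start of therapy, and none of these patients dies during follow-up.

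- Design rule: end of follow-up = max(end of therapy, 30, discharge).
- Data Collection rule: end of follow-up = min(entry + 30, discharge).

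| Entry | End of therapy | Discharge | Design rule ends | Data Collection rule ends |
|---|---|---|---|---|
| 2 | 10 | 12 | 30 | 12 |
| 2 | 42 | 14 | 42 | 14 |
| 2 | 20 | 50 | 50 | 32 |
| 5 | 10 | 12 | 30 | 12 |

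Under the Data Collection rule, the first, second and fourth patients have no planned day-30 status, and the second has no end-of-therapy status either. The fourth also shows a gap in the design rule. If the 30 days in Section 8.2 run from study entry, day 30 falls on 5 + 30 = day 35, but follow-up closes on day 30. The design rule fully covers 30-day mortality only if the origin is the start of therapy.

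**Size under the Data Collection rule.** The documents give no discharge or mortality rates, so all three inputs are assumptions:

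- d, share discharged alive before day 30: 0.20 to 0.60
- m, in-hospital death by day 30: 0.15 to 0.20
- q, death by day 30 among those discharged: 0.02 to 0.06

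Patients without planned status, 80 × d: 80 × 0.20 = 16; 80 × 0.60 = 48.

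*If they are counted as alive:*

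- Deaths missed, 80 × d × q: 80 × 0.20 × 0.02 = 0.32; 80 × 0.60 × 0.06 = 2.88.
- In percentage points, 100 × d × q: 0.4 to 3.6.
- Share of all 30-day deaths, dq/(m + dq): smallest 0.004/0.204 = 2.0%; largest 0.036/0.186 = 19.4%.

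*If they are dropped:* the estimate becomes m/(1 − d) against a true value of m + dq.

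| d | m | Estimate | True value (q = 0.02 to 0.06) | Inflation, points |
|---|---|---|---|---|
| 0.20 | 0.15 | 18.75% | 15.4% to 16.2% | 3.35 to 2.55 |
| 0.20 | 0.20 | 25.0% | 20.4% to 21.2% | 4.6 to 3.8 |
| 0.60 | 0.15 | 37.5% | 16.2% to 18.6% | 21.3 to 18.9 |
| 0.60 | 0.20 | 50.0% | 21.2% to 23.6% | 28.8 to 26.4 |

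The range over the whole grid is 2.55 to 28.8 points.

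**The case against.** The strongest reply is that Section 8.2 never says deaths in any location. If in-hospital death within 30 days was meant, stopping at discharge costs no 30-day data and the planned tests can be run. This stands as an open reading, and it makes the data loss conditional. It does not remove the contradiction, and the endpoint would then need to be named for what it is.

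A second reply is that the design text is plainly the intended rule. No section says so. A reader might go further and infer that this rule secures both mortality outcomes and that the difference in time origin is harmless. The documents do not support that: it holds only if the 30 days run from the start of therapy, which is nowhere stated.

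A third reply is that electronic records may show deaths after discharge. Some may appear there, but the Data Collection rule ends follow-up at discharge and no later look-up is planned. The absence of a recorded death is not confirmed survival.

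It is also fair to say that the outcome is secondary, that every rate above is assumed, and that the plan does not propose dropping patients. Withdrawal ("Once they have withdrawn from the study, all subsequent blood sampling and data collection will be discontinued") can add unknown status under either rule, but that is ordinary attrition and not part of this inconsistency.

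**Conclusion.** This is an internal inconsistency that should be fixed. The contradiction itself rests on no assumption. The loss of 30-day status rests on two conditions: that the Data Collection rule is followed, and that 30-day mortality includes deaths after discharge. Under the assumed rates it then affects 16-48 of about 80 patients. The resulting error depends on handling that the plan does not state: 0.3-2.9 missed deaths (0.4-3.6 points) if these patients are counted as alive, or an inflation of 2.55-28.8 points if they are dropped.

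A reader might infer that the study's main result is compromised or that the mortality analyses are impossible. The documents support neither. The primary outcome is target attainment, determined from drug levels sampled within dosing intervals and, under Section 5, no longer taken after discharge; it does not depend on day-30 status. The mortality analyses can be done under a rule and a definition that match; the plan has not yet fixed either.

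**What to change.** Replace the two sentences in Section 5 with one rule and one time origin, either start of therapy or a defined study entry, and use the same origin in Section 8.2. One workable form is to follow every patient to the later of end of beta-lactam therapy and day 30 from that origin, regardless of discharge, ending early only at death or withdrawal.

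In Section 8.2, state that 30-day mortality includes deaths after discharge. Name the source of vital status: the electronic record, or a call if the consent form covers it. Treat unknown status as missing, not as alive, and report how many patients it concerns. If only in-hospital follow-up is feasible, rename the endpoint in-hospital mortality.

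The cost is small: wording in the two places in Section 5 and in Section 8.2, and a day-30 status check for roughly 80 patients.
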